8.0 STUDY OBJECTIVES

8.1 PRIMARY OBJECTIVES

To determine if PGB can be combined with LFX to reduce opioid withdrawal-related subjective effects

8.2 SECONDARY OBJECTIVES

1) To determine if PGB plus LFX will result in more successful opiate detoxifications Successful detoxification is defined as completing the 7-day regimen/dosing of either PBG/LFX or LFX/PGB-PLA without leaving the inpatient unit or otherwise withdrawing from

the study; having a SOWS score of less than 6; a COWS score of less than 9; and a urine drug screen that is negative for opioids, **excluding buprenorphine**, **and fentanyl**.

2) To determine whether PGB plus LFX improves rates of completion of detox and receipt of XR-NTX

8.3 ASSESSMENT TOOLS USED TO ACHIEVE OBJECTIVES

The assessment tools used to achieve study objectives are in Table 1. Effectiveness and safety endpoints, based on these assessment tools, are defined in Section 9.2 and 9.4.

9.0 STUDY DESIGN

This study is a phase II, two-part randomized, double-blind placebo-controlled, study to assess the effectiveness of PGB combined with LFX to reduce opioid withdrawal- related subjective effects, and to examine whether a PGB/LFX combination can increase the proportion of opioid use disordered (OUD) subjects who transition to antagonist treatment (XR-NTX).

The study will use three sites, each with inpatient units that provide beds and care from nurses that will be trained in study procedures and dosing requirements. Each site will recruit around 30 randomized subjects, with the Mountain Manor Site and the PENN site possibly recruiting greater than 30 subjects, for a total sample size of 90, using DSM-5 to establish an OUD diagnosis with physiologic features. This trial has 4 distinct phases (see Figure 1 schematic): 1) Outpatient Screening; 2) Inpatient medication induction plus other assessments on Days 1-7; 3) Inpatient XR-NTX administration on Day 8 or 9; and 4) Outpatient Follow-Up (5 days). Total days in study is 15 days plus or minus the time taken to complete the initial outpatient screening assessments. Randomization will occur before inpatient admission.

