
Outpatient screening is used to determine eligibility for the study. It will consist of the 30 days prior to inpatient admission for study detoxification and treatment. On day 1 of inpatient treatment subjects will be randomized to PGB/LFX or PGB-PLA/LFX for a 7-day detoxification. On day 8, if the patient completes **Duration of subject** detoxification, continues to be interested in XR-NTX treatment, provides a urine, participation and and passes a naloxone challenge, he/she will be offered one injection of XR-NTX before hospital discharge. This injection of XR-NTX is optional. If retests must be medication administration done, such as a repeat of the naloxone challenge, all subjects are eligible to remain inpatient until Day 9. All subjects, whether they receive XR-NTX or not. will be referred to continuing care and asked to return to the research outpatient clinic on days 10 and 15 for follow-up visits. Subjects who cannot find a provider may be offered an additional XR-NTX injection up to 5 weeks after the Day 8 injection. Reference therapy PGB-Placebo plus lofexidine The primary outcome is reduction in subjective withdrawal as measured twice/day using the Short Opiate Withdrawal Scale (SOWS- Gossop). SOWS scores range from zero to 30. Groups will be compared on 10 or more repeated SOWS responses during inpatient treatment using linear mixed-effects regression models. The SOWS total will be regressed on a three-level factor for site, and a two-level factor for pregabalin dose, with random intercept and correlated residuals and a random slope included if necessary for fit. Contrasts Statistical between the combined groups will be estimated from this model. Methodology The secondary outcome is an ordinal response indicating completion of detox and receipt of antagonist treatment, with levels (1) failure to complete detox, (2) completion of detox with failure to receive antagonist treatment, and (3) completion of detox and receipt of antagonist treatment.

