5.0 Table 1. Overview of Study Assessments

Assessment	Outpatient	Inpatient	Inpatient	Inpatient					Inpatient	Outpat	Outpat	EOS/ AMA VISIT (early)
	Screen	Day 1	Day 2	Day 3	Day 4	Day 5	Day 6	Day 7	Day 8/9 [†] (all assessments Done both days Unless otherwise Stated)	Day 10 +2 business days	EOSDay 15 +2 business days	(04)
Informed Consent	1X											
Locator Information	1X									1X		
Medical History	1X											
Physical/Weight	1X										1X	1X
CBC* with Diff and PLT, INR	1X									1X INR Not repeated	1X if no D10 No INR	1X No INR
Blood Chemistry, with Magnesium and Calcium	1X									1X	CMP 1X IF No Day 10	1X No magnesi m
Creatine Kinase	1X								1X (done at D8- only)	ropodiou		1X
Estimated Glomerular Filtration	1X											
Child Pugh Score	1X											
Urinalysis with Reflex Microscopy	1X									1X		1X
Urine Pregnancy Test - F	1X	1X							1X (if done at D8-do not repeat on D9)		1X	1X
UDS	1X	1X							1X	1X	1X	1X

13

Assessment	Outpatient	Inpatient	Inpatient	Inpatient					Inpatient	Outpat	Outpat	EOS/ AMA VISIT (early)
	Screen	Day 1	Day 2	Day 3	Day 4	Day 5	Day 6	Day 7	Day 8/9 [†] (all assessments Done both days Unless otherwise Stated)	Day 10 +2 business days	EOSDay 15 +2 business days	
Fentanyl	1X	1X							1X	1X	1X	1X
xylazine	1X								1X	1X	1X	1X
Alcohol Breathalyzer Test	1X									1X	1X	
HEP B & C	1X											
ECG	1X	1X	1X	1X	1X	1X	1X	1X				
MINI	1X											
Inclusion/Exclusion	1X											
Randomization Form	1X											
Visual Analog Scale for Craving		2X	2X	2X	2X	2X	2X	2X	1X			
Insomnia Severity Index	1X	1X	1X	1X	1X	1X	1X	1X	1X	1X	1X	
SOWS-Gossop	1X	2X	2X	2X	2X	2X	2X	2X	1X	1X	1X	
COWS	1X	2X	2X	2X	2X	2X	2X	2X	2X	1X	1X	
POSS		3X	4X	4X	4X	4X	4X	4X	1X			
Naloxone Challenge (optional; only if pt. is interested and detoxed)									1X (if positive on D8- repeat on D9)			1X Can be given to AMA Pts
XR-NTX									1X (if not done D8- do on D9)			1X Can be given to AMA Pts
Vital Signs Cont'd next pg.	1X	8X	8X	8X	8X	8X	8X	8X	1X BP sitting only	1X BP sitting	1X BP sitting only	1X BP sitting

Assessment	Outpatient	Inpatient	Inpatient	Inpatient					Inpatient	Outpat	Outpat	EOS/ AMA VISIT (early)
	Screen	Day 1	Day 2	Day 3	Day 4	Day 5	Day 6	Day 7	Day 8/9 [†] (all assessments Done both days Unless otherwise Stated)	Day 10 +2 business days	EOSDay 15 +2 business days	
(BP-sitting & standing); Pulse										only		only

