This study is a phase II, double-blind placebo-controlled, study to examine whether: 1) PGB can be combined with LFX and reduce opioid withdrawal-related subjective effects; and, 2) if safe and effective, can the combination increase the proportion of OUD subjects who transition to XR-NTX. To investigate these objectives, preliminary data on the safety and tolerability of PGB/LFX dose sequencing, and the reduction of opioid withdrawal-related subjective effects, will be obtained in the current trial. We will use a two-arm comparison; PGB/LFX versus LFX/PGB-PLA. If the current trial shows that a PGB/LFX combination is likely to be safe effective, and reduces opioid withdrawal related subjective effects, we will conduct a second trial in which we will test the PGB/LFX combination in a larger sample, under well- powered conditions, to evaluate the results of the current trial in relation to the efficacy of the combination to reduce opioid withdrawal-related subjective effects and possibly increase the proportion of patients who complete detoxification and transition to XR-NTX treatment. The first 2-year component will utilize three sites with inpatient units. Each site will recruit around 30 randomized subjects for a total sample size of 90 using DSM-5 criteria to establish

OUD with physiologic features diagnosis.

This trial has 4 distinct phases (see 4.0: Figure 1 schematic): 1) Screening (up to 30 days before inpatient admission and randomization). Patients who were never randomized and who come back after 30 days must be reevaluated and assigned a new screening number; 2) Inpatient Detox (1 – 7) days for medication induction and other assessments, 3) Inpatient administration of XR-NTX (Day 8); and, 4) Outpatient Follow-Up (Day 10 and Day 15). Dosing for lofexidine and pregabalin will begin at 12:00 on day 1 and be tapered starting at day five. This plan will permit dose adjustments for adverse effects, such as BP <90 mmHg systolic or <60 mmHg diastolic, a clinically significant drop in standing vs sitting blood pressure, bradycardia <50 bpm, or excessive sedation. Subjects that need a procedure repeated can continue inpatient treatment through day 9. The Study Schema is seen above in 4.0, Figure 1: Overview of Study Schematics Pregabalin (LYRICA®) plus Lofexidine (LUCEMYRATM)". Study assessments are seen in 5.0 Table 1.

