9.1 GENERAL DESIGN

9.1.1 Phase 1: Outpatient Pre-Screening (Up to 30 days before hospital admission).

Study inclusion and exclusion criteria will be assessed to make sure the subject meets admission requirements. Those who meet requirements will be given information and details of the study including the timeline, potential risks and benefits, inpatient requirements, confidentiality, and told that participation is voluntary. They will be asked to read the informed consent and encouraged to ask questions, then given a quiz in which they must answer 9 of 10 answers correctly (three retries allowed). Potential subjects will then be asked to sign the informed consent and given a copy.

Once consented, subjects will be screened for up to 30 days to include the following: completion of a locator information form, concomitant medications used in the past 30 days, physical, medical history, complete blood cell count (CBC) with differential and PLT, INR, CMP with magnesium and calcium, urinalysis with reflex microscopy, urine drug screen, a fentanyl urine test, a xylazine urine test, a urine pregnancy test, ECG, creatine kinase test, an eGFR calculation, a Child-Pugh score (liver function), MINI assessment for Opioid Use Disorder with physiologic features (e.g. withdrawal), Insomnia Severity Index (ISI), Clinical Opioid Withdrawal Scale (COWS), Short Opioid Withdrawal Scale (SOWS-G), vital signs (can use manual blood pressure check if considered necessary), Timeline Follow- back (TLFB), Clinical Global Impression Scale (CGI), Hamilton Depression and Anxiety scales (HAM- D, HAM-A), Columbia-Suicide Severity Rating Scale (CSSR-S), an alcohol breathalyzer test, hepatitis B and C tests. Those meeting admission criteria will be asked to report to the inpatient unit on Monday through Friday; randomization will occur at hospital admission. Each collaborating program will enroll around 30 subjects, 20 to receive pregabalin plus lofexidine and 10 to receive placebo pregabalin plus lofexidine. The Pharmacy or designated physician or nurse at each site will receive pre-packaged blinded medications from PENN IDS. All study staff will be blinded.

9.1.2 Phase 2: Inpatient Detoxification (Days 1 thru 7).

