10.0 SUBJECT SELECTION AND DISCONTINUATION

All subjects will be recruited at the site level through newspaper and social media advertising, primary care practices and outpatient facilities, and community referrals. For a more detailed description of recruitment procedures, see section 10.3. Once a potential subject has been identified, a CRA or another study staff person will screen him/her for admission/exclusion criteria. For respondents that appear eligible and are interested in participating, an appointment will be made to come to the research facility and review study procedures, expectations, and other information in more detail. The CRA or another study staff person will explain the study and the potential subject will be asked to read the study enrollment consent, and encouraged to ask questions about anything that is unclear. Subjects still interested in participating will be asked to take a 10-item pre-enrollment guiz and correctly answer 9 of 10 true/false questions about the study to be eligible to continue (three additional tries permitted). A study physician, or other designated clinical staff person will do the medical history and physical. A nurse, physician, medical assistant or other designated personnel will draw blood for screening labs, arrange for an ECG whose results will be reviewed by the PI at the site, and if a problem is found, will transmit a copy to the Study Cardiologist, and/or the study Medical Monitor and/or the Lead Study PI to review before a decision is made as to the next step. If Cardiology is used, each site should have a decision sent back to the site within 24 hours. Upon confirmation that all medical and inclusion and no exclusion criteria are met, a study staff person will randomize the subject and make an appointment for admission to the collaborating inpatient unit.

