11.0 METHODS FOR ASSIGNING SUBJECTS TO TREATMENT GROUPS

11.1 RANDOMIZATION

[name] will develop a program using computer-generated, randomly permuted blocks within each site

that are stratified according to male/female. Upon completing screening assessments, research staff will request randomization be performed by the site research pharmacy. The patient will be sequentially assigned to the next treatment based on male/female status. At all sites, patient treatment will correspond to a unique randomization number.

Penn IDS will upload the randomization lists into a Treatment Unmasking Program, per IDS SOP-309. Access to this trial within the program will be provided to authorized Penn users. In the event of an emergency, unmasking can occur at any time using the subject's assigned randomization number. The user will not be unmasked to the treatment of other subjects. For other sites, [name] will give the randomization list to PENN IDS who will be responsible for maintaining the randomization blind.

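### Randomisation is placed both before admission and on Day 1, and is not tied to the first-dose criteria, so never-dosed patients can take some of the 90 places; the loss is probably small

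*Combined protocol and SAP*

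**What the plan says.** **Before admission.** Section 9.0: "Randomization will occur before inpatient admission". Section 10.0, once eligibility is confirmed: "a study staff person will randomize the subject and make an appointment for admission to the collaborating inpatient unit".

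**At admission or Day 1.** Section 9.1.1: "randomization will occur at hospital admission". Section 3.0: "On day 1 of inpatient treatment subjects will be randomized to PGB/LFX or PGB-PLA/LFX for a 7-day detoxification". Figure 1 heads the randomisation column as Day 1, hospitalised. Section 7.1.6 describes screening as "up to 30 days before inpatient admission and randomization". Section 9.1.2 has patients admitted, then randomised, then required to show withdrawal before dosing.

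**Ambiguous.** Section 11.1: "Upon completing screening assessments, research staff will request randomization be performed by the site research pharmacy". Table 1 has a "Randomization Form" row whose single mark appears to sit under Screen.

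**First-dose criteria.** Sections 7.3.1, 7.3.3 and 9.1.2 require COWS of at least 6 and SOWS of at least 4 before the first dose. Section 9.1.2 allows repeat scoring until they are met, with no time limit and no stated outcome for a patient who never meets them.

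**Counting and analysis.** Section 16.2 closes enrolment at 90 randomised. Sections 10.8, 13.6 and 19.2 analyse all randomised. Section 13.3.2 counts detoxification as complete only if a dose was received on day 7.

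**The concern.** Sections 9.0 and 9.1.1 cannot both be followed. Each of the three sites could choose a different section and still comply, so being randomised, and hence being in the intent-to-treat set, could mean different things at different sites.

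The places at stake are the 90 that close enrolment. There are two routes to a randomised patient who is never dosed:

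- **No-show.** Possible only if randomisation precedes admission. The patient supplies no inpatient SOWS. The return rule in section 7.1.6 does not help, since it covers "Patients who were never randomized and who come back after 30 days must be reevaluated and assigned a new screening number".
- **Admitted non-qualifier.** Possible under either timing, because randomisation is not conditional on the first-dose criteria.

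Both fall in the lowest level of the ordinal secondary outcome whatever their arm, which pulls the arms together. The non-qualifier may also add untreated Day 1 SOWS readings to the primary model.

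**Working it through.** **1. The plan's own power.** Inputs from section 13.2: 30 versus 60 patients, two-sided alpha 0.05, within-subject correlation 0.5, overall dropout 40%, and 80% power at d = 0.44 for group by linear time. That paragraph states neither the number of readings nor the shape of attrition. I took 14 readings (section 13.3.1), equal correlations, and retention falling linearly from 1 to 0.60. Generalised least-squares information summed over the dropout patterns gives a standard error of 0.1621 for the slope contrast, scaled as the difference at the last reading:

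- power = Φ(0.44/0.1621 − 1.960) = Φ(0.754) = 77.5%.

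With 15 readings the same model gives 79.8%. The stated 80% is thus reachable but depends on unstated inputs, and I do not call it wrong. Below, the model supplies only the relative loss, applied to the plan's 80%.

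**2. Never-dosed patients inside the 40% dropout.** The documents give no never-dosed share f, so f is an assumption. Retention now runs linearly from 1 − f to 0.60. With r = SE(0)/SE(f):

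- power = Φ(2.802 × r − 1.960), where 2.802 = 1.960 + 0.842;
- detectable d at 80% power = 0.44/r.

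| Assumed f | SE(f) | r | Power | Change (points) | Detectable d |
|---|---|---|---|---|---|
| 0 | 0.1621 | 1 | 80.0% | – | 0.440 |
| 1/90 | 0.1624 | 0.998 | 79.8% | −0.2 | 0.441 |
| 3/90 | 0.1631 | 0.994 | 79.5% | −0.5 | 0.443 |
| 5% | 0.1636 | 0.991 | 79.3% | −0.7 | 0.444 |

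The calculation gives never-dosed patients no inpatient readings, so it describes no-shows exactly and non-qualifiers only approximately.

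**3. Ordinal secondary outcome.** If f is equal in the two arms, the completion proportion in each arm is multiplied by 1 − f, and so is the difference. Illustration: 41% versus 61% among dosed patients. The 41% is the lofexidine completion rate quoted in section 7.1.5; the 61% is assumed.

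- f = 1/90: 20.0 × 0.989 = 19.8 points; odds ratio 2.25 becomes 2.23.
- f = 3/90: 20.0 × 0.967 = 19.3 points; odds ratio 2.19.
- f = 5%: 20.0 × 0.95 = 19.0 points; odds ratio 2.16.

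**4. Primary model and non-qualifiers.** Section 9.1.2 schedules the first Day 1 SOWS before any dose, so that reading is untreated for everyone. Only later readings from a non-qualifier differ from those of dosed patients. A few such readings early in the week could slightly attenuate the slope contrast.

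**The case against.** Only sections 9.0 and 10.0 say before admission. Section 11.1 sets an earliest point and is compatible with Day 1. The Table 1 mark comes from a table flattened in extraction, and shows where a form is filed rather than when allocation happens. The procedural sections already agree on admission or Day 1. All of this stands, and it makes the correction short. It does not remove the contradiction, because section 10.0 is itself an operative instruction.

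Non-qualifiers may be few: section 10.1 requires opioid use on at least 20 of the last 30 days, and section 9.1.2 allows retesting. This also stands. Randomising at admission and analysing everyone randomised is a legitimate design, so allocating after the criteria are met is a preference, not a necessity.

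Section 10.9 has patients who miss an appointment re-contacted, and section 19.2 keeps randomised patients in study activity. This helps with follow-up, but neither section states a route to a later admission under the same allocation.

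A reader might infer a substantial loss of power by assuming a large never-dosed share, or by adding it on top of the 40%. The documents support neither. They give no such rate, and section 13.2 describes its 40% as overall dropout, which most naturally includes these patients. The gap between 77.5% and 79.8% from one unstated input, the number of readings, is larger than any effect in the table.

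**Conclusion.** The contradiction is real, in current text, and should be corrected. The missing link between randomisation and the first-dose criteria is a secondary gap that choosing Day 1 does not close by itself.

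The statistical cost is probably small: about 0.2 to 0.7 points of power, and 0.2 to 1.0 points off an illustrative 20-point completion difference, for assumed never-dosed shares from 1 in 90 to 5%. These figures rest on equal shares in the two arms, linear attrition, 14 equally correlated readings and calibration to the stated 80%.

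Two stronger readings should be avoided. One is that the primary result is materially biased: no-shows add no inpatient SOWS, and non-qualifiers can add only a few untreated readings. The opposite one, that the primary estimate is wholly unaffected, is also too strong because of those readings. The main reason to act is that all three sites should randomise at the same point.

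**What to change.** - Change sections 9.0 and 10.0 to one time, Day 1 in the unit before the first dose, and clarify section 11.1 and the Table 1 row to match. Sections 3.0, 7.1.6 and 9.1.1 and Figure 1 already fit.
- Preferably, reorder section 9.1.2 so that allocation follows documentation of the existing COWS and SOWS criteria, with thresholds and repeat testing unchanged. If so, extend section 10.7, whose definition names only inclusion criteria, so that admitted non-qualifiers are listed with the screen failures.
- Keep the analysis on all randomised patients and add to section 13.6 that never-dosed patients are reported by arm.

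**Cost.** Wording changes and site retraining. If allocation follows scoring, there is a practical burden: section 9.1.2 puts both scoring and the first dose around 12:00, so the pharmacy request and pack release must fit the existing Day 1 window in section 7.3.3.1, and some first doses may move to the next scheduled time. The intent-to-treat set would then describe patients who had qualified for dosing. Early losses after randomisation would still be possible.

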9.1 GENERAL DESIGN

9.1.1 Phase 1: Outpatient Pre-Screening (Up to 30 days before hospital admission).

Study inclusion and exclusion criteria will be assessed to make sure the subject meets admission requirements. Those who meet requirements will be given information and details of the study including the timeline, potential risks and benefits, inpatient requirements, confidentiality, and told that participation is voluntary. They will be asked to read the informed consent and encouraged to ask questions, then given a quiz in which they must answer 9 of 10 answers correctly (three retries allowed). Potential subjects will then be asked to sign the informed consent and given a copy.

Once consented, subjects will be screened for up to 30 days to include the following: completion of a locator information form, concomitant medications used in the past 30 days, physical, medical history, complete blood cell count (CBC) with differential and PLT, INR, CMP with magnesium and calcium, urinalysis with reflex microscopy, urine drug screen, a fentanyl urine test, a xylazine urine test, a urine pregnancy test, ECG, creatine kinase test, an eGFR calculation, a Child-Pugh score (liver function), MINI assessment for Opioid Use Disorder with physiologic features (e.g. withdrawal), Insomnia Severity Index (ISI), Clinical Opioid Withdrawal Scale (COWS), Short Opioid Withdrawal Scale (SOWS-G), vital signs (can use manual blood pressure check if considered necessary), Timeline Follow- back (TLFB), Clinical Global Impression Scale (CGI), Hamilton Depression and Anxiety scales (HAM- D, HAM-A), Columbia-Suicide Severity Rating Scale (CSSR-S), an alcohol breathalyzer test, hepatitis B and C tests. Those meeting admission criteria will be asked to report to the inpatient unit on Monday through Friday; randomization will occur at hospital admission. Each collaborating program will enroll around 30 subjects, 20 to receive pregabalin plus lofexidine and 10 to receive placebo pregabalin plus lofexidine. The Pharmacy or designated physician or nurse at each site will receive pre-packaged blinded medications from PENN IDS. All study staff will be blinded.

9.1.2 Phase 2: Inpatient Detoxification (Days 1 thru 7).

Subjects are admitted to the inpatient unit, randomized to one of the two study medication conditions, and will need to demonstrate withdrawal before starting study medications by having a COWS >/= 6 and a SOWS >/= 4. LFX and PGB dosing will begin at 12:00 on day 1 and a study drug taper will be done from days 5-7. Dose times follow the schedule outlined above and adjustments will be made based on BP changes and/or other AEs. Administration of LFX will be withheld or reduced in cases of dizziness or lightheadedness, clinically significant hypotension and/or the BP changes described above. We will explain to participants the importance for adequate oral hydration during the consenting process and throughout the detox. Similar procedures will be applied to PGB in cases of excessive sedation, dizziness, peripheral edema, or other problematic side effects that appear related that medication.

Dosing schedules are in Tables 2 and 3. Assessments for Day 1 through 7 include:

- 1) ECG is obtained before the 12:00 dose of study medications on Day 1 and before the 08:00 dose of study medications on Day 2-7
- 2) VAS is given before the first dose of study medication at 12:00 on Day 1 and before the 16:00 dose on Day 1. On Day 2-7, the VAS is given before the first dose of study medications at 08:00 and before the 16:00 dose of study medications
- 3) ISI given before the 12:00 dose of study medications on Day 1, and before the 08:00 dose of study medications on Days 2-7
- 4) COWS is given around 12:00 on Day 1 before the first dose of study medication; and around16:00 before the next dose of study medication. If subject is admitted without the requisite withdrawal (COWS >/= 6 and SOWS >/= 4), subsequent COWS and SOWS can be administered before the first dose of study medication until dosing criteria is met.
- 5) SOWS-G is given around 12:00 on Day 1 before the first dose of study medication; and around 16:00 before the next dose of study medication
- 6) POSS is given prior to all doses (08:00, 12:00, 16:00 and 20:00) of study medication
- 7) Sitting and standing blood pressure and pulse are taken prior to each dose of study medication and 1 to 2 hours after dosing, (can use manual blood pressure check if considered necessary)
- 8) Weight taken 1x at screen and Day 15 and recorded on the physical form
- 9) Adverse events/SAEs recorded daily
- 10) Concomitant medication records reviewed and recorded each day
- 11) C-SSRS is given at the end of each study day
- 12) Comfort medications given on a PRN schedule

Successful detoxification is defined as (a) not leaving the inpatient unit before day 8; (b) SOWS of 5 or less and COWS of 8 or less; and, (c) urine drug screen negative for opioids, excluding buprenorphine, and fentanyl.

